Overview

A cluster randomised controlled study with longitudinal follow up of SARS-CoV-2 infection in 120 households which have newly diagnosed positive cases. The index cases and their HHC will be invited and enrolled after informed consent. Baseline surveys and SARs-CoV-2 screening (PCR and IgM/IgG serology) and then weekly SARs-CoV-2 screening (PCR and serology) of HHC will occur at 0, 1, 2, 3 and 4 weeks. The households will be randomized to an intensified COVID19 infection mitigation intervention (n=60) administered by CHWs vs the standard messaging (n=60). Please see Figure 1 for a schematic overview of the study design.

EUC = enhanced usual care

Figure 1: Flow chart and schematic overview of the study design.

Sample Size Determination

We calculated the different effect sizes (Table 1). Based on exponential test for comparing hazards, assuming $120*6=720$ subjects, different intraclass correlation coefficients (ICCs) and comparing $R_0=2.5$ (with resulting incidence of 0.208 among 720 subjects) to a reduced R_0 of 0.9 (64% reduction, with resulting incidence of 0.075 among 720 subjects) or 1.25 (50% reduction) or 1.5 (40% reduction).

Table 1: ICC calculations

ICC	R0 2.5 to 0.9	R0 2.5 to 1.25	R0 2.5 to 1.5
	64% reduction	50% reduction	40% reduction
0.05	1.00000	1.00000	0.999944
0.25	1.00000	0.999891	0.991312
0.50	0.999993	0.995042	0.935880
0.75	0.999729	0.972942	0.846222
0.90	0.999033	0.951485	0.792745

Randomization and stratification

After completing consent, households will be randomised in a 1:1 ratio in blocks of 10 (60 households per group; 360 patient and household contacts per group).

Overview of data and data sources for analysis

All data are collected with two individual identifiers: study ID and PID (Western Cape Government health number). The exception is data source #4, which only uses PID.

1. Redcap database
 - a. Baseline survey of index patient and household characteristics (demographics, COVID-19 symptoms, household tracing information, home/dwelling characteristics that impact transmission (size, rooms, ventilation, access to safe water, laundry facilities))
 - b. Uptake of infection control measures at all follow-up contacts (assessment of use of isolation measures and cleaning of household surfaces up to 10 days post case of last diagnosis in household, at 1, 2, 3, 4 weeks).

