4. STUDY OUTCOMES

4.1. Primary study outcomes

- The incidence rate of SARS-CoV-2 infections among HHC of the index COVID19 cases over a 4 week period
- The time to transmission to HHC during that time period
- The association between the time to transmission and clinical symptoms of the index cases
- The symptomatic/asymptomatic ratio among transmitted SARS-CoV-2 in household contacts
- The proportion of transmissions to HHC in the enrolled households of COVID cases assigned to the infection mitigation intervention arm compared with the households in the enhanced usual care (EUC) arm.

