5. GENERAL PRINCIPLES OF ANALYSIS

The statistical analysis plan will be finalised and signed-off prior to database lock. Post-hoc analysis (analyses performed that are different from those described in the final version of the SAP) will be documented in the final report.

Descriptive summaries will be presented using summary statistics (e.g. number (n), mean, standard deviations (SD), median, minimum, maximum) and 95% confidence intervals (CI) for continuous parameters or frequency distributions (n, %) for categorical parameters.

In general, all households who entered the study will be included in the statistical evaluation (intention-to-treat analysis). Households who completed the final screening will be included in the per-protocol analysis. There will be no predefined interim statistical analysis or stopping rules.

All output will be generated using STATA SE Version 13 or R. No missing data will be replaced, and it will be shown in any summaries as missing.

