6.3. Demography and Baseline Characteristics

Demographic data and baseline characteristics of index clients, households and household contacts will be summarized. Summary statistics will be adjusted for clustering by household.

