7. ANALYSIS OF PRIMARY STUDY OUTCOMES

7.1. The proportion of SARS-CoV-2 transmitted to HHC of the index COVID19 cases over a 4 week period

SARS-CoV-2 infection in a HHC will be defined as a positive PCR or evolving positive serologic test in a HHC who had a negative PCR or negative serology at baseline. The incidence of SARS-CoV-2 infection in HHC will be calculated as the number of new cases divided by the person time at risk and 95% confidence intervals calculated based on the Poisson distribution adjusted for clustering by household. This incidence as well as the timing to transmission will be analysed using exponential shared frailty models taking the clustering by household into account and allowing for censoring. The start time will be the date of diagnosis of the index case and the event time the date of diagnosis of the HHC using the date of the first positive test based on PCR or serology. Models will include possible confounders including adjustment for baseline values.

7.2. The proportion of transmissions to HHC in the enrolled households of index COVID cases assigned to the infection mitigation intervention arm compared with the households in the enhanced usual care (EUC) arm.

The incidence of SARS-CoV-2 will be estimated for the different study arms and incidence of and timing to SARS-CoV-2 per study arm will be compared by including study arm in the exponential frailty models.

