8.5. The symptomatic/asymptomatic ratio among transmitted SARS-CoV-2 in household contacts

The proportion of symptomatic and asymptomatic transmitted SARS-CoV-2 infections will be calculated, overall, with 95% confidence intervals based on binomial or asymptotic normal distributions.

8.6. The incidence of SARS-CoV-2 transmitted to HHC of the index COVID19 cases over a 4 week period, stratified by COVID-19 wave.

The incidence of SARS-CoV-2 will be compared by COVID-19 wave using exponential frailty models and including an indicator of the wave in the model.

The COVID19 wave will be defined as follows:

- wave 1: date of diagnosis of index case between 1 May and 31 November
- wave 2: date of diagnosis of index case from 1 December onwards

8.7. Analysis of household exposure to SARS-CoV-2 at baseline using the baseline serology result, and development of antibodies using the serology result during follow-up.

Longitudinal weekly prevalence profiles of serology results will be summarized overall and by study arm. These profiles can be analysed using hierarchical mixed effect logistic regression models with both household and HHC as nested random effects. Time to development of antibodies can be analysed using exponential frailty models. Models will include baseline serology results.

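### SAP 8.5 states no household adjustment for the 95% interval on the symptomatic proportion, although SAP 7.1 adjusts the incidence interval for clustering

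*SAP*

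**What the plan says.** SAP 4.1 lists "The symptomatic/asymptomatic ratio among transmitted SARS-CoV-2 in household contacts" among the primary outcomes. Its analysis is in section 8, with the secondary outcomes. SAP 8.5 calculates the proportions over all transmitted infections, "with 95% confidence intervals based on binomial or asymptotic normal distributions". It names no variance adjustment.

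Other parts of the SAP treat clustering as follows:

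- **7.1 (incidence among contacts):** "95% confidence intervals calculated based on the Poisson distribution adjusted for clustering by household".
- **6.3 (demography and baseline):** "Summary statistics will be adjusted for clustering by household".
- **8.7 (serology profiles):** "hierarchical mixed effect logistic regression models with both household and HHC as nested random effects", but only as a model that can be used. The weekly summaries themselves carry no clustering term.
- **8.3 (psychosocial scores):** linear regression, with no household term named.
- **Section 5 (general principles):** 95% intervals for continuous parameters and "frequency distributions (n, %) for categorical parameters". It contains no general clustering rule.

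The protocol's sentence on clustering, under Statistical Analysis and sample size, concerns the incidence of new cases. Neither that sentence nor 6.3 reaches 8.5.

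**The concern.** Infected contacts are nested in households. Members of one household share exposure, may share characteristics that influence whether infection produces symptoms, and may report symptoms alike. If symptom status is correlated within households, the infected contacts carry less information than the same number of independent people. An interval that treats them as independent is then too narrow.

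The symptomatic share is part of protocol Specific Aim 1 and is one of the protocol's stated questions. It is an estimate, not a test, so the interval is its only statement of precision. The clean contrast is with 7.1: both sections report one estimate with a 95% interval on contacts from the same households, and only 7.1 states an adjustment.

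**Working it through.** SAP 8.5 states no figure to reproduce. The question is how far a naive interval would be off.

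**Inputs from the SAP**

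- There are 120 households, 60 per arm.
- The sample-size section gives R0 = 2.5 "with resulting incidence of 0.208 among 720 subjects". This equals 2.5 × 60 / 720 = 0.208, that is, one arm's infections divided by both arms' subjects. R0 = 1.5 (the 40% reduction) gives 1.5 × 60 / 720 = 0.125 in the same way.
- With 360 per arm as denominator, the same R0 values give 2.5 × 60 / 360 = 0.417 and 1.5 × 60 / 360 = 0.25. Both readings are carried through.
- Infection ICC ρ: 0.05 and 0.25, from SAP Table 1.
- Contacts at risk per household, n: 6 if all 720 are contacts; 5 if the six include the index ("60 households per group; 360 patient and household contacts per group").

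**Assumptions**

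- n = 4 is added because 7.1 counts only contacts who are negative at baseline.
- Symptom ICC: 0.05, 0.10, 0.25 and 0.50. The documents give none.
- Symptomatic share: 60%, used only for widths in percentage points and for the simulation.

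**Formulas**

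- Infected contacts per affected household, weighted by infections: m(p) = 1 + (n − 1)(p + ρ(1 − p)), averaged over the two arms with weights proportional to p.
- Design effect: DE = 1 + (m − 1) × symptom ICC.
- Excess of true over naive SE: √DE − 1.
- Coverage of a nominal 95% Wald interval: 2Φ(1.96/√DE) − 1.

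**Smallest case** (n = 4, incidence 0.208 / 0.125, ρ = 0.05)

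- m(0.208) = 1 + 3 × (0.208 + 0.05 × 0.792) = 1.743
- m(0.125) = 1 + 3 × (0.125 + 0.05 × 0.875) = 1.506
- m = (0.208 × 1.743 + 0.125 × 1.506) / 0.333 = 1.654

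**Largest case** (n = 6, incidence 0.417 / 0.25, ρ = 0.25)

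- m(0.417) = 1 + 5 × (0.417 + 0.25 × 0.583) = 3.814
- m(0.25) = 1 + 5 × (0.25 + 0.25 × 0.75) = 3.188
- m = (0.417 × 3.814 + 0.25 × 3.188) / 0.667 = 3.579

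The other ten combinations fall between these two.

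| Symptom ICC | DE | Excess SE | Wald coverage (formula) |
|---|---|---|---|
| 0.05 | 1.033-1.129 | 1.6-6.3% | 94.6-93.5% |
| 0.10 | 1.065-1.258 | 3.2-12.2% | 94.2-91.9% |
| 0.25 | 1.164-1.645 | 7.9-28.2% | 93.1-87.4% |
| 0.50 | 1.327-2.290 | 15.2-51.3% | 91.1-80.5% |

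**In percentage points.** Expected infections are 60 × n × (sum of the two incidences), from 60 × 4 × 0.333 = 80 to 60 × 6 × 0.667 = 240. The naive half-width 1.96 × √(0.6 × 0.4 / infections) then runs from 10.7 down to 6.2 points. Multiplying by √DE − 1 case by case, the missing half-width is 0.2-0.4, 0.3-0.8, 0.8-1.9 and 1.6-3.5 points at the four symptom ICCs.

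**Simulation check.** Infection and symptom status were drawn as beta-binomial in 120 households, with 6,000 trials for each of the twelve combinations at each symptom ICC.

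- Wald coverage agreed with the formula to within about one point. At symptom ICC 0 it was 94.2-95.3%, so the naive interval is then adequate.
- The exact binomial interval covered about 1 to 3 points more than Wald: 93.9-96.0% at symptom ICC 0.05, and 88.7-94.6% at 0.25.
- A household-robust interval on the logit scale covered 94.4-95.5% in every cell, including those at symptom ICC 0.

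**The case against.** Four points can be made against the concern.

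- **The wording does not forbid an adjustment.** Asymptotic normal names a reference distribution, not a variance estimator, so a normal interval with a household-robust SE also complies. This stands. The defect is that 8.5 leaves the choice open where 7.1 closes it.
- **The size depends on a parameter that the documents do not give.** The ICCs in SAP Table 1 concern infection, so their upper values (to 0.90) cannot be read as symptom ICCs. At a symptom ICC of 0.05 to 0.10 the missing half-width is under one percentage point. This stands, and it limits the weight of the point.
- **Little hangs on the interval.** It is descriptive, its outcome is not named in the primary objectives in SAP 2.1, and no test or arm comparison uses it. This stands too, although 4.1 does list the outcome as primary.
- **8.5 is not a lone exception.** A reader might infer that every other section handles clustering. The documents do not support that: 8.3 names no household term, the household model in 8.7 is optional, and 6.3 covers baseline summaries only. The contrast rests on 7.1.

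A reader might also infer that any positive correlation takes the interval below 95%. That is too strong, because 8.5 permits an exact binomial interval, whose conservatism roughly offsets the loss at a symptom ICC of 0.05.

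**Conclusion.** The concern holds as a gap in specification with a modest and uncertain effect. An analyst can follow 8.5 to the letter and report an interval that ignores households, and nothing else in the SAP or protocol corrects this.

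On the stated assumptions the loss is slight at symptom ICCs of 0.05 to 0.10 and material from about 0.25, where the SE is 8-28% too small and Wald coverage is about 87-93%. At 0.50 the figures are 15-51% and about 80-91%. An infection ICC above 0.25, which Table 1 also considers, would enlarge the effect; fewer contacts at risk would reduce it.

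It would be wrong to read this as a threat to the estimated proportion or to the comparison of STOPCOV with enhanced usual care. Neither uses this interval.

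**What to change.** In SAP 8.5, keep the overall proportion across all infected contacts and state that its 95% interval allows for household clustering, as 7.1 does for incidence. A suitable implementation is a cluster-robust SE on the logit scale, from an intercept-only GEE or a survey-type linearised variance with household as the cluster. The back-transformed intercept of a random-intercept logistic model should not be used without marginalising, because it is conditional on household and is not the overall proportion.

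The cost is one phrase in the SAP and about one line of code in STATA or R, with no new data. Section 5 has the SAP finalised before database lock, so the change fits that step. The downside is a somewhat wider interval, and almost none if symptom status proves uncorrelated within households.

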8.8. Process Evaluation Analysis

All interviews will be transcribed verbatim, and the analysis of qualitative data will be iterative, moving between data collection and data analysis to test emerging theories. It may for example emerge that some households have experienced significant stigma with their COVID-19 diagnosis, and this may shape their experience of the intervention, and require deeper exploration. The analysis of observational data will therefore require knowledge from the counsellors' interviews to compare how reported experiences relate to actual implementation and acceptability of the intervention. Care will be taken to identify and follow up 'deviant cases' which do not fit into emerging theories.

By setting the delivery of the STOPCov intervention within a macro, meso and micro contextual framework, we will be able to make the transition from the identification of patterns within households, to theoretical explanations of how different structural relations and mechanisms impact on intervention delivery and outcomes. Identifying 'telling cases' will facilitate generalizable inferences and predictions on how best to optimise the STOPCov intervention.
